### **8.3.6 Summary of Safety Data**

Summary of safety data will be based on the Safety Population. Safety parameters include adverse events, N (%) patients progressing to AML, laboratory parameters, vital signs, ECG parameters, prior and concomitant medication use. For each safety parameter, the last assessment made prior to the first dose of study treatment will be used as the baseline, unless otherwise specified. In general, safety data will be summarized descriptively; no inferential statistical procedures will be applied.

Adverse events will be coded using Medical Dictionary for Regulatory Activities (MedDRA). A treatment emergent adverse event (TEAE) is defined as any new or worsening of an existing condition occurred after the first dose of the study medication and within 28 days after the last dose of study medication. TEAEs will be tabulated to examine their frequency, severity, organ systems affected and relationship to study treatment. Deaths, SAEs, AEs leading to study or treatment discontinuation, and AEs of special interest will be listed or tabulated separately.

Laboratory tests, vital sign measurements, ECG parameters, as well as the changes from baseline will be summarized descriptively by assessment time point. Clinically significant changes from baseline in these safety parameters will be identified. Shift tables will summarize changes for selected laboratory measures.

Medications used prior to and during the study will be coded using The World Health Organization Drug Dictionary (WHODrug). Prior and concomitant medications will be tabulated by therapeutic class and generic name.

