14.1. Adverse Events

A treatment-emergent AE (TEAE) is defined as an AE that begins on or after the first dose of study treatment and within 28 days of the end date of the last dose of study treatment. An adverse event with unknown onset date will be counted as TEAE unless the event is resolved prior to the first dose of study medication.

Adverse events will be coded using the Medical Dictionary for Regulatory Activities (MedDRA, version 19.1). CTCAE Version 4.03 will serve as guidance for specific severity assessment criteria for AEs. Any adverse event recorded prior to the start of study treatment will be listed together with all other adverse events. Only treatment-emergent adverse events will be summarized.

If a patient has more than one TEAE coded to the same preferred term, the patient will be counted only once for that preferred term. Similarly, if a patient has more than one TEAE within a system organ category, the patient will be counted only once in that system organ category.

In this analysis, if a patient reports multiple occurrences of TEAEs within one system organ class or preferred term, the most closely related occurrence will be presented. TEAEs with unknown relationship to study treatment will be counted as “possibly related” in the summary table but will be listed with a missing relationship in data listing.

In this analysis, if a patient reports multiple occurrences of TEAEs within one system organ class or preferred term, the most severe occurrence will be presented in the table summarized by maximum severity. TEAEs with unknown severity will be counted as “Severe” in the summary table but will be listed with a missing severity in data listing.

The overview table by treatment and overall will be summarized showing the number and percentage of patients with at least one AE in any of the following categories:

- TEAEs
- drug related (Possibly Related and Related) TEAEs
- all grade 3 or greater TEAEs
- Serious TEAEs
- TEAEs leading to discontinuation of study treatment
- TEAEs leading to death
- TEAE of special interest

In summary, the following sets of adverse events will be summarized separately in separate tables by SOC (sorted alphabetically) and PT (sorted by descending) that present the number and percentage of patients with:

- any TEAE (number of patients who have at least one adverse event)

- TEAE by maximum severity
- TEAE with relationship to study medication suspected to be related to study drug

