- all grade 3 or greater TEAE
- treatment-emergent serious AEs (TESAE)
- TEAEs leading to discontinuation of study treatment,
- TEAEs leading to death
- TEAE of special interest
- TESAE leading to discontinuation of study treatment

AE of special interest consists of the following categories: Secondary hypothyroidism, Thyroid disorders (Hypothyroidism and Hyperthyroidism), Dermatitis Exfoliative Generalised, Deep vein thrombosis, Pulmonary embolism, Cardiovascular events (cardiac failure, arrhythmia, myocardial infarction), Seizures, Serious infections. Number and percentage of patients with any TEAE of special interest will be summarized up to 28 weeks, 52 weeks and 52 weeks and beyond. Exposure adjusted incidence rate (EAIR) of TEAE of special interest per 100 patient exposure years will also be presented. See [Section 14.1.2](#) for EAIR calculation.

In addition, most frequently occurring adverse events ($PT \geq 5\%$ of patients in any dose cohort/treatment group) and most frequently occurring non-serious adverse events ($PT \geq 5\%$ of patients in any dose cohort/treatment group) for each PT will be summarized in descending frequency according to its incidence in either dose cohort/treatment group.

In addition, the incidence rate $\times 100 / PEY$ will be presented along with the number and percentage of patients in double-blind tables, where Patient-Exposure-Year (PEY) = (Last Dose Date - First Dose Date + 1)/365.25.

All AEs will be presented in a listing, including patient identifier, treatment group, system organ class, preferred term, start and stop dates, seriousness, severity, relationship to study treatment, Action taken with regard to study drug and outcome. Additionally, listings of SAEs, Death and AEs leading to permanent discontinuation of study drug and AEs of special interest will be presented. The listing of AEs prior to start of treatment will be provided for all patients enrolled.

Listings of death report will be provided in the SAF with death date, primary cause of death and verbatim, system organ class and preferred term of AE leading to death.

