14.1.2. Exposure Adjusted Incidence Rate

Exposure adjusted incidence rate EAIR (per 100 patient years at risk) will be calculated regarding selected TEAEs of interest.

The exposure adjusted incidence rate (per 100 patient years at risk) will be calculated as follows:

$$\frac{\text{Number of subjects with event}}{\text{Person - years at risk}} \times 100$$

Where total cumulative time at risk is the sum of individual time at risk.

1. The Time at Risk for a subject with the event of interest will be calculated (in years) as:

$$(\text{First event date} - \text{analysis Date of first dose} + 1) / 365.25$$

Where 'Analysis Date of first dose' is defined as the date of initial dose of the study drug.

2. The Time at Risk for a subject without the event of interest is calculated as

$$(\text{Censoring date} - \text{Date of first dose} + 1) / 365.25$$

Censoring date will be calculated as:

Min (death date, last contact date if the subject is lost to FU, visit date of week 52 + 28, last dose date + 28)

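### TEAE rates per patient-exposure-year count events to 28 days after the last dose but divide by dosing time alone, which distorts them more in the arm with shorter exposure

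*SAP*

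**What the plan says.** SAP 14.1 defines a treatment-emergent event as one that begins on or after the first dose and "within 28 days of the end date of the last dose of study treatment". Protocol 8.3.6 sets the same limit: "within 28 days after the last dose of study medication". Only treatment-emergent events are summarised.

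SAP 14.1 then adds a rate per 100 PEY, which "will be presented along with the number and percentage of patients in double-blind tables". Its denominator is "Patient-Exposure-Year (PEY) = (Last Dose Date - First Dose Date + 1)/365.25", so it stops at the last dose. The section does not say whether the numerator is patients or events. For the frequency tables, a patient with repeated events under one preferred term is treated as follows: "the patient will be counted only once for that preferred term". The same applies within a system organ class.

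SAP 14.1.2 defines a second rate, the EAIR, which "will be calculated regarding selected TEAEs of interest". Time at risk runs to the first event. For patients without the event it is censored at "Min (death date, last contact date if the subject is lost to FU, visit date of week 52 + 28, last dose date + 28"), which matches the treatment-emergent window. SAP 14.1 applies the EAIR to events of special interest. SAP 14.3 and 14.5 extend it to laboratory and vital-sign abnormalities if dropout differs between the arms.

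**The concern.** A rate should divide events by the time in which they could have been counted. Here the numerator has a 28-day tail and the denominator has none. The tail will hold data: under Protocol 4.3 and 6.4, patients who stop early have a visit four weeks later, and Protocol Appendix B continues adverse event recording after end of treatment.

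The size of the mismatch depends on how long patients are dosed. Exposure adjustment is meant to make arms with different follow-up comparable, yet this rate is distorted most when exposure differs. Unequal stopping is possible: lack of efficacy is a listed reason for discontinuation in Protocol 4.3, and the SAP itself provides for differential discontinuation.

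There is also a labelling problem. SAP 14.1 calls the EAIR a rate per 100 patient exposure years, while SAP 14.1.2 calls it a rate per 100 patient years at risk. An event of special interest could appear with two different rates under nearly the same name.

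**Working it through.** The documents give no rate, event count or mean exposure for this point, so there is no figure to reproduce. The mean exposures and hazards below are assumptions.

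**Inputs.** Tail of 28 days (SAP 14.1, Protocol 8.3.6). Denominator from first to last dose (SAP 14.1). Maximum treatment of 52 weeks, or 364 days (SAP 3.1). One count per patient per term (SAP 14.1).

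**1. Same numerator, matched window.** With N events and D mean dosing days, the planned rate is proportional to N/D and the matched rate to N/(D + 28). Their ratio is (D + 28)/D = 1 + 28/D, wherever in the window the events fall.

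| Mean dosing | D | Factor |
|---|---|---|
| 52 weeks | 364 | 392/364 = 1.077 |
| 40 weeks | 280 | 308/280 = 1.100 |
| 28 weeks | 196 | 224/196 = 1.143 |
| 16 weeks | 112 | 140/112 = 1.250 |

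These are upper bounds, since they give every patient a full 28-day tail. Death, loss to follow-up, or still being on drug at the Week 28 cutoff shortens or removes it.

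**2. Between arms, equal true rates.** Divide the factor of the shorter-exposure arm by that of the longer one:
- 40 v 52 weeks: 1.100/1.077 = 1.021
- 28 v 40 weeks: 1.143/1.100 = 1.039
- 28 v 52 weeks: 1.143/1.077 = 1.061
- 16 v 40 weeks, a more extreme assumption: 1.250/1.100 = 1.136

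Assume instead exponential discontinuation with 20% and 40% stopped by Week 28. Mean dosing over 52 weeks is then about 42.6 and 33.5 weeks, the factors are 1.094 and 1.119, and the ratio is about 1.02. If data are cut at Week 28 for everyone and patients still dosing have no tail, the factors are 1.032 and 1.073, a ratio of 1.04.

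**3. One count per patient.** PEY then also runs on after the first event, which lowers the rate. Assume a constant hazard λ per year and the same D for all patients. The PEY rate is [1 − exp(−λ(D + 28)/365.25)]/(D/365.25), and the EAIR is λ.

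| λ per year | 52 weeks: affected | PEY/EAIR | 28 weeks: affected | PEY/EAIR |
|---|---|---|---|---|
| 0.05 | 5.2% | 1.049 | 3.0% | 1.126 |
| 0.2 | 19.3% | 0.969 | 11.5% | 1.076 |
| 1 | 65.8% | 0.660 | 45.8% | 0.854 |

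The two rates agree when about 14% of patients are affected at 52 weeks' dosing, or about 24% at 28 weeks. Above that, the PEY rate is the lower one. At every hazard tried, the PEY/EAIR ratio is higher with shorter exposure. At λ = 1 the contrast between 28 and 52 weeks is 0.854/0.660 = 1.29. The omitted tail supplies 1.061 of this, and the remaining 1.29/1.061 = 1.22 comes from counting time after the first event.

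**The case against.** The strongest reply is that the rates are not inflated in general. A reader might infer from the window mismatch that every rate is too high and that correcting it lowers them all. The documents do not support that. The rate sits beside the number and percentage of patients, and each patient counts once per term, so the natural numerator is patients. Rows such as any TEAE, or a common system organ class, may then lie below the EAIR. What stands is narrower: for a given numerator the denominator is too short.

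A reader might also infer that roxadustat is made to look safer. That would require placebo patients to stop earlier, and the documents do not say which arm does. If roxadustat patients stop earlier, the distortion runs against the drug.

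Two further replies stand in full. Events of special interest already have the EAIR, whose time at risk includes the 28 days. And Protocol 8.3.6 makes safety summaries descriptive with no inferential procedures, so no test depends on these rates. It can also be said that two openly defined measures may legitimately differ. That would be a fuller answer if the labels kept them apart, which they do not.

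**Conclusion.** The mismatch is real and follows from the SAP's own definitions. It raises the rate for a given numerator by at most 7.7% at 52 weeks' mean dosing and 14.3% at 28 weeks. Between arms with equal true rates, the omitted time produces a spurious ratio of about 1.02 to 1.06 if mean exposures lie between 28 and 52 weeks, with the direction unknown. These figures assume a full tail for every patient and assumed mean exposures. For common terms counted once per patient, time after the first event pulls the level the other way, and the net rate may fall below the EAIR. The point does not touch the EAIR, the counts and percentages, or any hypothesis test. Severity is minor.

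**What to change.** Before database lock, make one of two changes to the PEY rate in SAP 14.1:

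- End PEY at the SAP 14.1.2 censoring date: the earliest of death, last contact for patients lost to follow-up, the Week 52 visit plus 28 days, and the last dose plus 28 days. Truncate it at the data cutoff as well for the Week 28 analysis. This is the smaller change and removes the window mismatch. It leaves exposure running past the first event.
- Use the SAP 14.1.2 time at risk for every exposure-adjusted TEAE table, with the same cutoff truncation. This removes both effects and gives each event a single rate.

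In either case, state that the numerator is patients with an event, and use one label for the rate in 14.1 and 14.1.2.

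The cost is SAP wording and minor reprogramming, with no new data and no effect on power or type I error. Rates for less common events will fall. If the 14.1.2 time at risk is adopted, rates for common events will rise: in the λ = 1 example at 52 weeks, from about 66 to 100 per 100 patient-years.

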14.1.1. AE Subgroup Analysis

The overview table of TEAE by the following subgroups will be provided:

- by gender: male, female
- by age: < 65 , ≥ 65 years
- by race: white, non-white
- by baseline endogenous EPO level: ≤ 200 mIU/mL, > 200 and ≤ 400 mIU/mL (defined as an exploratory endpoint in Section 12.3.4.3)
- by IPSS-R risk category: low risk / very low risk, intermediate risk
- by RBC transfusion burden: 1 pRBC/8-weeks over 16 consecutive weeks, 2- 4 pRBC/8-weeks

- by region: North America, Europe and Asia-pacific

In addition, for NDA filing in China, the overview table of TEAE, TEAE table and TESAE table by the following subgroups will be provided:

- by additional race subgroup: Asian, non-Asian
- by additional region subgroup: East Asia, non-East Asia

14.1.2. Exposure Adjusted Incidence Rate

Exposure adjusted incidence rate EAIR (per 100 patient years at risk) will be calculated regarding selected TEAEs of interest.

The exposure adjusted incidence rate (per 100 patient years at risk) will be calculated as follows:

$$\frac{\text{Number of subjects with event}}{\text{Person - years at risk}} \times 100$$

Where total cumulative time at risk is the sum of individual time at risk.

1. The Time at Risk for a subject with the event of interest will be calculated (in years) as:

$$(\text{First event date} - \text{analysis Date of first dose} + 1) / 365.25$$

Where 'Analysis Date of first dose' is defined as the date of initial dose of the study drug.

2. The Time at Risk for a subject without the event of interest is calculated as

$$(\text{Censoring date} - \text{Date of first dose} + 1) / 365.25$$

Censoring date will be calculated as:

Min (death date, last contact date if the subject is lost to FU, visit date of week 52 + 28, last dose date + 28)

14.2. Disease Progression of AML

The number and percentage of patients in double-blind component who progressed to AML will be presented in a frequency table using safety population.

Listings by patient with progressive disease for OL high-erythropoietin component and double-blind component will also be provided.

14.3. Clinical Laboratory Data

Summary tables for clinical laboratory data will be performed for double-blind component only.

The results of laboratory assessments, which include CBC, Serum chemistries (sodium, potassium, chloride, bicarbonate, BUN, creatinine, glucose, calcium, magnesium, phosphorus, lactate dehydrogenase (LDH), albumin) will be provided by a central laboratory. All summaries will be based on the standard units provided by the central laboratory.

Descriptive statistics for laboratory values (in SI units) and changes from baseline at each assessment time point will be presented by treatment group for laboratory parameters collected in the study.

To assess potentially clinically significant (PCS) laboratory abnormalities (Table 5), the number and percentage of patients with post-baseline lab values outside a pre-defined range (low or high) or limit of change will be tabulated. Laboratory test values will be considered PCS if they meet the criteria listed in the table. The number and percentage of patients with post-baseline PCS values will be tabulated. The

percentages are to be calculated relative to the number of patients with available non-PCS baseline values and at least one post-baseline assessment. The numerator is the total number of patients with at least one post-baseline PCS value. Shift tables may be presented.

Patient incidence for each abnormality will be calculated based on patients with a baseline value and at least one post-baseline value for criteria requiring baseline or patients with at least one post-baseline value for criteria not requiring baseline. If differential dropout is observed between the two treatment arms, then the exposure adjusted incidence rate EAIR (per 100 patient years at risk) will be calculated regarding each abnormality.

A supportive listing of patients with post-baseline PCS values will be provided including the patient ID, study center, baseline, and post-baseline values. Values from unscheduled time points will not be used in post-baseline analysis but will be listed.

In addition, for serology testing and other lab test (e.g. PT, PTT, Vitamin B₁₂ and folate) will be provided in data listings by patient. Local hemoglobin data will be listed along with prescribed dose adjustment for reference.

Table 5: Range of Potentially Clinically Significant Lab Values

Parameter	SI Unit	Lower Limit	Higher Limit
CHEMISTRY			
Alanine Aminotransferase (ALT)	U/L		≥3 * ULN
Alkaline Phosphatase (ALP)	U/L		≥3 * ULN
Aspartate Aminotransferase (AST)	U/L		≥3 * ULN
Calcium	mmol/L	<0.8*LLN	>1.2 * ULN
Creatinine	μmol/L		> 1.5x Baseline Value
Potassium	mmol/L	<0.75*LLN	>1.2 * ULN
Sodium	mmol/L	<0.9*LLN	>1.1 * ULN
Total Bilirubin	μmol/L		>1.5 * ULN
Urea (BUN)	mmol/L		>1.5x Baseline Value
CBC			
Neutrophils	10 ⁹ /L	≤1	
Platelet Count	10 ⁹ /L	≤ 100	≥700
White Blood Cell Count	10 ⁹ /L	≤2.5	≥15
LLN: Lower limit of normal, value provided by the laboratory			
ULN: Upper limit of normal, value provided by the laboratory			

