5.5. Baseline Measures and Change from Baseline

For patients who achieved $\geq 50\%$ reduction in number of pRBC transfusions over any 8 weeks (day 1 to week 52) compared to their baseline, the baseline will be calculated based on the transfusions within 8 or 16 weeks prior to the first dose.

For subjects with transfusion records within 16 weeks prior to first dose: Baseline number of transfusions (pRBC/8-weeks) = total number of packs of red blood cells within 16 weeks prior to first dose/2.

For subjects with transfusion records within only 8 weeks prior to first dose: Baseline number of transfusions (pRBC/8-weeks) = total number of packs of red blood cells within 8 weeks prior to first dose.

For other measurements, baseline value will be defined as the last measure taken before any study drug administration unless otherwise specified.

Change from baseline is defined as the difference between the baseline value obtained and the respective post-baseline time point for the continuous variables. Negative values represent decreases from baseline; positive values reflect increases from baseline.

Percent change from Baseline is defined as the change from Baseline divided by the Baseline value, multiplied by 100:

$$100 \times (\text{Post-Baseline value minus Baseline value}) / (\text{Baseline value})$$

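### SAP 14.3 takes patients already abnormal at baseline out of the denominator of the laboratory PCS percentage but leaves them in the numerator, which inflates rates for fixed-threshold parameters, chiefly blood counts

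*SAP*

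**What the plan says.** SAP 14.3 plans a table of PCS laboratory values with cut-offs in Table 5: "Laboratory test values will be considered PCS if they meet the criteria listed in the table". Two consecutive sentences define the percentage.

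- Denominator: percentages are taken "relative to the number of patients with available non-PCS baseline values and at least one post-baseline assessment".
- Numerator: "The numerator is the total number of patients with at least one post-baseline PCS value". No baseline condition is attached.

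The next paragraph gives a second base: "Patient incidence for each abnormality will be calculated based on patients with a baseline value and at least one post-baseline value" where the criterion needs a baseline, "or patients with at least one post-baseline value for criteria not requiring baseline". Neither branch removes patients who are PCS at baseline, and the section does not say which rule governs the table. The same paragraph also holds the rule that brings in exposure-adjusted incidence rates (EAIR) if dropout differs between the arms.

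Of the 12 parameters in Table 5, ten have fixed limits. Creatinine and BUN are judged against the patient's own baseline (for creatinine, "> 1.5x Baseline Value"). Under SAP 5.5, "baseline value will be defined as the last measure taken before any study drug administration unless otherwise specified".

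**The concern.** A non-PCS-baseline denominator is the usual base for treatment-emergent abnormality: among patients free of the abnormality at the start, how many develop it? The numerator does not answer that question. It also counts patients who were abnormal before the first dose and stayed so, and those patients are missing from the denominator.

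The exposed parameters matter in this disease. Protocol section 2 describes MDS by its cytopenias. Table 5 flags platelets at 100 or below, neutrophils at 1 or below and white cells at 2.5 or below (all 10⁹/L). A haematological safety table built this way could report mainly pre-existing disease while appearing to report new events. Two programmers could also produce different tables from the same section.

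**Working it through.** The SAP states no figure for this point, so there is none to reproduce.

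**Which parameters are exposed**

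- Creatinine and BUN: a baseline value cannot exceed 1.5 times itself, so nobody is PCS at baseline and there is no inflation.
- ALT, AST and total bilirubin: Protocol 4.2, exclusion 8, removes ALT or AST above 3 × ULN and bilirubin above 1.5 × ULN. These nearly match the Table 5 limits, so few patients should be PCS at baseline.
- Platelets, neutrophils and white cells: Protocol 4.1 and 4.2 (Amendment 02, the version available) set no numerical limit. The key criteria summarised in SAP 4.2.1, written for Amendment 03, name none either. In Appendix G, good cytogenetics (1), blasts of 2% or less (0), Hb below 8 (1.5), platelets below 50 (1) and ANC below 0.8 (0.5) total 4.0. That is intermediate risk, so such a patient meets the risk-group criterion.
- ALP, calcium, potassium and sodium also have fixed limits. The documents give no reason to expect many baseline-PCS patients there.

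**Algebra**

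Let b be the share of an arm that is PCS at baseline, r the share of those who are PCS again later, and i the incidence among the rest. Assume everyone has later data.

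- As written: [i(1−b) + r·b] / (1−b) = i + r·b/(1−b).
- Numerator limited to the denominator population: i.
- The written figure exceeds 100% when b > (1−i)/(1−i+r).
- Baseline disease makes up most of the numerator when r·b > i(1−b), that is, b > i/(i+r).

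**Numbers (i = 10%; r = 0.8 and 1.0; all assumed)**

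| b | r = 0.8 | r = 1.0 | Nested numerator |
|---|---|---|---|
| 10% | 10 + 0.8 × 11.1 = 18.9% | 10 + 11.1 = 21.1% | 10% |
| 20% | 10 + 0.8 × 25 = 30.0% | 10 + 25 = 35.0% | 10% |
| 30% | 10 + 0.8 × 42.9 = 44.3% | 10 + 42.9 = 52.9% | 10% |

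- Passing 100% needs b above 0.9/1.7 = 53% (r = 0.8) or 0.9/1.9 = 47% (r = 1.0).
- Baseline disease dominates the numerator once b exceeds 0.1/0.9 = 11% (r = 0.8) or 0.1/1.1 = 9% (r = 1.0).

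**In whole patients**

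SAP section 17 reports 140 patients enrolled in the double-blind component. At 3:2 that is 84 and 56. With 84 patients and b = 20%, 17 are PCS at baseline and 67 are not; 7 of the 67 become PCS. As written the table shows 21/67 = 31.3% (14 of the 17 PCS again) or 24/67 = 35.8% (all 17). The nested figure is 7/67 = 10.4%.

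**The case against.** The best defence is that the denominator sentence comes first and sets the population, so the numerator can be read as counting within it. A careful programmer might do that. But the numerator sentence refers to the total number of patients, and the following paragraph supplies a different base without ranking the two. The text does not settle the matter.

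Other points for the plan stand in part. Protocol 8.3.6 makes safety summaries descriptive and says shift tables will cover selected laboratory measures, although SAP 14.3 leaves them optional. SAP section 8 summarises baseline platelet counts by arm. SAP 14.3 also plans changes from baseline by visit and a listing with baseline and later values. A reader could work out what happened, but not from the percentage itself.

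Three stronger readings are tempting and not supported:

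- *The table will show impossible percentages.* That needs about half an arm PCS at baseline. The documents give no baseline prevalence; Appendix G shows that low counts are possible, not how common they are.
- *All laboratory percentages are wrong.* Creatinine and BUN are immune, and the three liver parameters nearly so.
- *The table will create a false drug effect.* That needs the arms to differ in b. If b were 25% against 15% with i = 10% in both, the table would show 43.3% against 27.6% at r = 1.0, or 36.7% against 24.1% at r = 0.8. This shows what an imbalance would do, not that one exists.

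**Conclusion.** The point holds as a defect of definition. SAP 14.3 specifies a ratio whose numerator is not contained in its denominator, and the next paragraph adds a conflicting base. The inflation is r·b/(1−b): about 9-11 percentage points at b = 10%, 20-25 at 20% and 34-43 at 30%, for r between 0.8 and 1.0. All of b, r and i are assumptions, and the inflation shrinks towards nothing as b does.

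The practical exposure is platelets, neutrophils and white cells. The consequence is confined to descriptive safety tables. The primary endpoint and the sequence of secondary tests are not affected, and no laboratory PCS table is among the Week 28 tables in SAP Appendix 19.9. It should be corrected before the final safety tables are produced.

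**What to change.** 1. In SAP 14.3, define the numerator as those patients in the stated denominator (baseline not PCS, with later data) who then have a PCS value. State that this rule governs the PCS table.
2. Replace the competing patient-incidence sentence, but do not delete the whole paragraph: it contains the EAIR rule for differential dropout. Keep that rule and apply it to the same at-risk patients.
3. Commit to shift tables for platelets, neutrophils and white cells, so that patients PCS at baseline stay visible.
4. In the same edit, reconcile SAP 14.3, which leaves unscheduled values out of post-baseline analysis, with Appendix 19.3.1, which uses every post-baseline assessment to determine PCS status.

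Dropping the non-PCS condition from the denominator, as SAP 14.5 does for vital signs, would also give a valid proportion. It suits vital signs because Table 6 requires a change from baseline, so a baseline reading cannot be PCS. For fixed laboratory limits it would mix existing disease with new events: in the 84-patient example with r = 1.0 it gives 24/84 = 28.6%, against 7/67 = 10.4% for new abnormality.

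The cost is SAP wording, a table-shell note and three shift tables. No new data are needed.
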